This project presents an innovative proposal, addressing a BCG vaccine with known efficacy against severe TB in childhood and reliable for the use of adjuvant therapy in patients with malignant bladder neoplasia.

BCG is an easily accessible vaccine, widely used by SUS in newborn children, thus facilitating its incorporation into a new preventive proposal for COVID-19. In addition, the selection of health professionals will be based on diagnostic screening and confirmatory tests of COVID-19.

It is intended to analyze the role of BCG in the prevention of infection and also in the occurrence of severe forms of COVID-19 in addition to evaluating the immune response mediated by this vaccine in voluntary health professionals.

GOALS:

In the period of 6 months, to analyze the effect of BCG as a protective factor for COVID-19 in research volunteers, aiming at greater efficiency in the prevention of subjects at high risk of infection and evolution to severe forms of the disease, as well as to evaluate the specific and non-specific immune responses to SARS-CoV-2 in vaccinated and unvaccinated volunteers who evolved with COVID-19 or not.

Primary Objectives:

1. Assess the impact of BCG vaccine administration on the cumulative incidence of SARS-CoV-2 infection
2. Assess the impact of BCG vaccine administration on the cumulative incidence of severe forms of COVID-19
3. Evaluate the bcg vaccine-mediated immune response in volunteers

Secondary Objectives:

In groups receiving BCG or placebo, infected and not infected with SARS-CoV-2:

- Epidemiological:

1. Estimate whether BCG vaccination compared to placebo prolongs the time to the first respiratory disease proven by SARS-CoV-2;
2. Estimate whether BCG vaccination compared with placebo reduces the proportion of symptoms associated with COVID-19 (fever or at least one sign/symptom of respiratory disease);
3. Estimate whether BCG vaccination compared to placebo reduces absenteeism (missing days) in volunteers who are health professionals;
4. Analyze the safety of BCG vaccination in adult volunteers;

- Laboratories:

5. Describe the inflammatory profile by dosing neutrophils, platelets, cit-H3, alpha 1 antitrypsin (α 1AT), galectin-2, ferritin, transferrin-R, glycated hemoglobin (HbA1c),

C-reactive protein (CRP), D-dummer, LDH, albumin and hemosedimentation velocity (ESR);

6. Describe the profile of inflammatory cytokines identified in the BCG and placebo groups, comparing to the protective events to SARS-CoV-2;

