Participants who present some test results collected during the study outside the normal range will be evaluated by the study physician. It should be indicated in the participant's folder that this result has been verified and whether or not there is clinical significance. If any, the participant should be referred for specialist evaluation at the hospital where his follow-up is being carried out.

Visits	Evaluations	Exams	Procedures
Screening or Recruitment	Face-to-face assessment of eligibility criteria, application of the TCLE	NASOarchyeal swab RT-PCR, anti-SARS-Cov-2 antibody levels, BHCG dosage and HIV serology	Invitation to participate in the study, application of the TCLE, collection of clinical samples (nasopharangeal swab and blood).
Inclusion or M0 0 day of preventive treatment (ToT) (BCG or placebo)	Face-to-face assessment with confirmation of eligibility, clinical inclusion visit, collection of exams and dose of BCG or placebo	IGRA; Complete blood count, lipidogram, albumin, HbGlic, LDH, PCR, ESR, D-D-Dmer; and biomarkers*.	Nursing and medical consultation. Collection of clinical sample (blood). Application of preventive treatment.
S1 - S12 7-90 days of preventive TTO (±3 days)	Telephone and/or SMS contact, and/or weekly email and sending photo of the injection site	No exams	Fever questionnaires and/or respiratory signs and symptoms and photo submission of the injection site
M1 10 days of preventive TTO (±5 days)	Face-to-face visit to the laboratory for blood collection for biomarkers	Anti-Anti-SARS-Cov-2 antibody levels; Complete blood count, lipidogram, albumin, HbGlic, LDH, PCR, ESR, D-D-Dmer; and biomarkers*.	Collection of clinical sample (blood).
M3 90 days of preventive TTO (±14 days)	Face-to-face clinical visit for follow-up and blood collection for serology	Anti-Anti-SARS-Cov-2 antibody levels	Nursing and/or medical consultation. Collection of clinical sample (blood).
M4/M5 120/150 days of preventive Tom (±14 days)	Telephone contact and/or SMS, and/or weekly email	No exams	Fever questionnaires and/or respiratory signs and symptoms
M6 180 days of preventive TTO (±14 days)	Face-to-face clinical visit to close the study and for blood collection for serology	Anti-Antibody levels anti-SARS-Cov-2.	Nursing consultation. Collection of clinical sample (blood).
Fever and/or respiratory signs and symptoms	Face-to-face visit to the Worker's Health sector of its study center to collect exams	RT-PCR	Clinical sample collection (swab and blood).

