	Face-to-face clinical visit to the study center since asymptomatic and 14 – 30 days after the onset of symptoms	Anti-Anti-SARS-Cov-2 antibody levels; Complete blood count, lipidogram, albumin, HbGlic, LDH, PCR, VHS, D-Dallin and biomarkers*.	Nursing or medical consultation. Copy of the tests performed during COVID-19 infection. Collection of clinical sample (blood).

Subtitles: M0: Moment zero; S1-S12: Weeks 1 to 12; M1: Moment 1; M3: Month 3; M4: Month 4, M5: Month 5; M6: Month 6; *Clinical Analyses and Biomarkers: Will be performed only in hucff-idt ufrj, HUPE-PPC UERJ centers.

Storage of specimens during study visits:

The nasopharinal swab will be *obtained for the realization of the real time – polymerase chain reaction* (RT-PCR) for COVID-19. The collection will be performed using the technique described in the Manual of the Ministry of Health. The collection should be performed with the rubbing of the swab in the posterior region of the nasal caress trying to obtain some of the mucosal cells. The swab will be stored in 15ml tubes containing DMEM + Fetal Bovine Serum 10% + L-Glutamine Solution–Penicillin–Streptomycin.

After collection, the specimen will be packed in a refrigerator of specimens from the research center with temperature control between 2 - 8 °C.

Blood collection will comply with the guidelines of the Ministry of Health in the Manual Techniques for Blood Collection (2001) for the performance of blood count, lipidogram, albumin, LDH, ESR, C-reactive protein, D-dimmer and dosage of biomarkers described in the study protocol. The collected material will be distributed in 11 blood tubes [1 SST tube, 2 EDTA tubes – purple cap (4.5ml/each), 1 serum tube - red cap (4 ml/each), 1 gel activator tube - yellow cap (4 ml/each), 2 tubes with soric heparin - green cap (8 ml/each) and 1 Tempus tube – blue cap (3 ml/each)]. During the *screening or recruitment* visit, blood will be collected for BHCG dosage and HIV serology. In the inclusion visit the material will also be sent for IGRA [4 tubes Kit IGRA (1ml/each)].

After collection, the specimen will be packed in a refrigerator of specimens from the research center with temperature control between 2 - 8 °C.

All specimens will be delivered to their destination laboratories, transported in thermal boxes maintaining the necessary refrigeration and obeying the criteria of storage and maintenance of the viability of the collected material.

Procedure for applying bcg or placebo vaccine:

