According to CNS Resolution No. 441 of 2011 (Art. 1) and Ordinance MS No. 2,201 of 2011 (Art. 3), any organized collection of human biological material collected for scientific research purposes, including samples intended for routine examinations in a clinical trial (e.g., blood count and renal function) are considered as constituents of a biorepository or biobank. The biological material will be used as provided for in the research protocol, with no further future analyses different from those foreseen. If there is a proposal for future use of the stored samples, approval in the CEP/CONEP system will be required and a new protocol and TCLE will be submitted so that each participant can choose whether or not to allow the use of the samples for future studies.

Statistical Analysis Plan:

The primary efficacy analysis will compare the cumulative incidence of SARS-CoV-2 infection and the cumulative incidence of severe forms of COVID-19.

These analyses will occur when the last enrolled research subject has completed 30 days and 6 months of preventive treatment and will be performed using the results of COVID-19 diagnostic tests, as well as the data available in participating hospitals and national electronic notification systems of COVID-19. A modified treatment intention analysis (MITT) and protocol (PP) will be performed. The safety and tolerability analysis will consist of all patients who have been randomized and received a dose of the vaccine or placebo. Based on serum immune response concentrations, we will calculate certain immunoinflammatory variables related to the use of BCG versus placebo among subjects infected and not infected by COVID-19 among the categories with COVID-19 vaccine (Coronavac® or Covishield®) and without covid-19 vaccine.

The intervention and control groups will be compared at the time of inclusion in the study in relation to sociodemographic, clinical, radiological and biochemical imaging variables, in order to evaluate the adequacy of the randomization process. Multivariate

analyses using logistic regression or Poisson models with robust variance will be used to evaluate the effect of BCG vaccine on primary and secondary outcomes. Associations will be expressed in the form of risk ratios and respective 95% confidence intervals. Data imputation may be required and the *random forest system* will be used. Statistical software R, version 10.0.

Sample size:

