We will also use for the two outcomes the sequential design the groups are followed up until there is a group with clear benefits or that both groups do not present difference. This design is used when the results need to be known very quickly. If there is a large difference between the treatments, then this study will be performed in a shorter time when compared to the parallel trial. The main ethical advantage is that if one treatment shows a superiority over the other, the study can already be stopped. However, the

interim analyses will be previously planned, in such a way that the calculation of sample size allows the multiplicity of the tests. The meaning of p-values in sequential analyses also changes, because when using sequential analyses, more than one analysis is performed, and the typical definition of a p-value as data "at least as extreme" as observed needs to be reset. One solution is to sort the p-values of a series of sequential tests based on the downtime and at what time the test statistic was in a certain appearance, known as ordering.

3. Assess the BCG vaccine-mediated immune response in healthcare professionals

SARS-CoV2 infection is estimated to occur in approximately 20% of health professionals vaccinated by BCG (experimental group), in 30% of health professionals not vaccinated by BCG (placebo group) and not vaccinated for COVID-19 and in 15% in COVID-19 vaccinated without BCG vaccine. A reduction of 10% to 15% of the joint effect of bcg vaccine with Covid-19 vaccine is expected.

In this scenario, with the bearing of 376 health professionals in each arm, if we assume that the percentage of covid-19 vaccinated is 80% and equal in each arm, SARS-CoV2 infection is expected to be detected in 15 professionals vaccinated only with BCG, in 23 professionals not vaccinated with BCG and COVID-19 vaccine, 45 professionals vaccinated for COVID-19 without bcg vaccine and 38 professionals vaccinated for COVID-19 and BCG. For each subgroup (vaccinated and not vaccinated with BCG) it will be possible to identify the predictive biomarkers of infection by comparing infected professionals with those who were not infected with SARS-CoV2.

INTERIM ANALYSIS PLAN:

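### Immune response (primary outcome 3) is continuous, but the only models named for the BCG effect are logistic or robust Poisson with risk ratios, and the pre-dose M0 value is not named as a covariate

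*Combined protocol and SAP*

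**What the plan says.** All references are to the combined protocol and SAP.

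- **Status of the outcome.** Primary Objectives, item 3: "Evaluate the bcg vaccine-mediated immune response in volunteers". Outcomes, Primary Outcome, item 3: "Assess the BCG vaccine-mediated immune response in healthcare professionals".
- **Scale of the data.** Statistical Analysis Plan: "Based on serum immune response concentrations, we will calculate certain immunoinflammatory variables related to the use of BCG versus placebo". The sentence goes on to subdivide by infection and COVID-19 vaccine status. It names no marker, time point or model.
- **Models.** The same section, on multivariate models, says that "analyses using logistic regression or Poisson models with robust variance will be used to evaluate the effect of BCG vaccine on primary and secondary outcomes". The effect measure follows: "Associations will be expressed in the form of risk ratios and respective 95% confidence intervals".
- **Sampling.** In the Study visits table, the M0 row lists "IGRA; Complete blood count, lipidogram, albumin, HbGlic, LDH, PCR, ESR, D-D-Dmer; and biomarkers". The M1 row (day 10, ±5 days) is a "Face-to-face visit to the laboratory for blood collection for biomarkers" and repeats the clinical panel and biomarkers. The M3 and M6 rows list serology only. The table's footnote on clinical analyses and biomarkers reads "Will be performed only in hucff-idt ufrj, HUPE-PPC UERJ centers".
- **Stated uses of M0.** The Statistical Analysis Plan compares the arms at inclusion to check the randomisation. Laboratory Procedures, Immunoassays, lists M0 in the time scheme for relating markers to the blood count.

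**The concern.** A risk ratio is a measure for a yes/no outcome. Applied literally to a concentration, the modelling sentence leaves the analyst either to choose a cut-point that the plan does not supply, or to fit a model whose estimate is not the stated effect measure. Either choice would be open until the data are seen. For a listed primary outcome, that leaves the result dependent on an unplanned decision and may cost precision.

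The second part concerns a value that the trial already collects. People differ in inflammatory markers before any dose. In this trial, some of that spread may come from earlier COVID-19 vaccination: Inclusion criterion 4 admits people who completed the full schedule at least 15 days earlier, and the sample-size text expects 80% of the cohort to be COVID-19 vaccinated. Unless M0 enters the model for the BCG effect, between-person variation that has nothing to do with the randomised dose stays in the residual.

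**Working it through.** **The plan's own figure.** There is none for this outcome: no SD, effect size, cut-off, power or sample size. The 376 per arm is sized on infection (30% versus 20%). It serves here only as an upper bound, because biomarkers are measured at two of three centres.

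**Assumptions, not in the documents.** The marker is normal on the analysis scale (for example after taking logs). The M0-M1 correlation ρ is 0.3, 0.5 or 0.7. The number per arm with biomarkers is 250, with 188 and 376 shown as a range. Power is 80% and type I error 5%, as in the plan's sample size; two-sided testing is assumed.

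**Step 1, cost of a cut-point, if one were used.** Let a share p of participants lie above the cut c. The efficiency relative to comparing means is f(c)² / [p(1−p)], where f is the normal density.
- p = 0.50: (1/2π) / 0.25 = 2/π = 0.637, a loss of about 36%.
- p = 0.25: 0.539.
- p = 0.10: 0.342.

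The median is the best of these cuts, and this loss does not depend on ρ.

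**Step 2, gain from M0.** Adjustment multiplies the residual variance by 1 − ρ².
- ρ = 0.3: 0.91, a 9% cut, worth 1/0.91 = 1.10 times the participants.
- ρ = 0.5: 0.75, a 25% cut, worth 1.33 times.
- ρ = 0.7: 0.51, a 51% cut, worth 1.96 times.

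**Step 3, detectable difference in SD units.** For unadjusted M1, d = (1.96 + 0.84) × √(2/n). Divide by √0.637 for a median split, or multiply by √(1 − ρ²) for M0 adjustment. With n = 250:
- unadjusted M1: 2.80 × √(2/250) = 0.25
- median split: 0.25 / 0.798 = 0.31
- M0-adjusted: 0.25 × 0.954 = 0.24; × 0.866 = 0.22; × 0.714 = 0.18

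| n per arm | Median split | M1 unadjusted | Adjusted, ρ 0.3 | Adjusted, ρ 0.5 | Adjusted, ρ 0.7 |
|---|---|---|---|---|---|
| 188 | 0.362 | 0.289 | 0.276 | 0.250 | 0.206 |
| 250 | 0.314 | 0.251 | 0.239 | 0.217 | 0.179 |
| 376 | 0.256 | 0.204 | 0.195 | 0.177 | 0.146 |

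**Step 4, check on power.** Take 376 per arm and a true difference at which the M0-adjusted model has 80% power. Unadjusted M1 then has 76%, 68% and 52% power at ρ = 0.3, 0.5 and 0.7. A median split has 57%, 49% and 36%. A simulation of 1,500 trials per setting, using a log risk ratio with robust variance for the split, gave 58%, 50% and 35% for the split.

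**The case against.** The strongest reply is that the modelling sentence was written for the binary outcomes. The Statistical Analysis Plan opens by confining the primary efficacy analysis to infection and severe COVID-19, and concentrations get a separate sentence with no model. Study Design places the inflammatory profile in a coupled observational study of two cohorts. The text under Primary Outcome 3 compares markers between infected and uninfected participants, a question for which logistic regression is suitable. Much of this stands, and it limits what can be said:

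- A reader might infer that the sponsor plans to dichotomise the markers. No section says so or gives a cut-point. Robust Poisson can be fitted to a non-negative continuous outcome, where it estimates a ratio of means. The 36% loss is therefore conditional on a split, not a property of the plan.
- A reader might infer that M0 is used nowhere. It is used to check randomisation and is listed in the Immunoassays time scheme. The models are called multivariate with no covariate list, which neither includes nor excludes M0.
- A reader might extend the point to secondary objectives 5, 6 and 8. These ask for description or characterisation, so the point rests on primary outcome 3.
- At ρ = 0.3, M0 adjustment hardly moves the detectable difference (0.24 against 0.25 SD).

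The reply does not remove the problem. The sentence as written covers all primary outcomes, immune response is one of them, and no other model for the BCG effect on it appears anywhere. A ratio of means from a Poisson model would also not be the stated risk ratio. It is fair to add that outcome 3 names no marker, and that choosing a model does not cure that.

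**Conclusion.** The point holds as a mismatch between outcome and model, together with a baseline covariate that is collected but not named for the BCG effect. It does not hold as a claim that the plan dichotomises its markers or ignores M0 altogether.

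The two losses should be kept apart. The first arises only if a cut-point is used: at least 36% of the information for a normal marker, and more away from the median. The second arises if M0 is left out of the model. It ranges from small (9% of residual variance) to large (51%) over assumed correlations that the documents do not give. The SD figures also rest on an assumed number per arm; the relative losses do not.

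The change is worth making because it concerns a listed primary outcome and uses samples already scheduled. It does not touch the infection or severe-disease analyses.

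**What to change.** In the Statistical Analysis Plan:

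1. Limit the logistic/Poisson sentence and the risk-ratio sentence to binary outcomes.
2. For continuous markers under primary outcome 3, specify linear regression of log(M1) on randomised arm, log(M0) and centre, reported as a geometric mean ratio (BCG to placebo) with 95% CI.
3. State a rule for values below the detection limit, since the log scale cannot take zeros.

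While editing, name the principal marker or markers and how multiplicity across the panel is handled. Also reconcile M1 as the analysis time with the M0, M1, M3 and M12 scheme under Immunoassays, because the Study visits table schedules the full panel only at M0, M1 and the visit after COVID-19.

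The cost is SAP wording and routine analysis code, settled before unblinding. No new samples or visits are needed.

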7. Describe the epigenetic alterations associated with monocytes and neutrophils related to the protection of COVID-19;
8. Characterize the cell population (T, B lymphocytes, neutrophils and monocytes) in peripheral blood of the study groups (BCG and placebo);
9. Relate the profile of immune response associated with mild and severe forms observed in the study groups (BCG and placebo);
10. Analyze the serum concentration of antibodies and relate it to the immune response;
11. Identify possible antibodies that may confer immunity to new COVID-19 infections;
12. Perform transcriptomic analysis of neutrophilic, lymphocytic and monocytic responses in the study groups (BCG and placebo) involved in the modulation of immune responses in the study groups;
13. Identify predictive biomarkers of infection and/or illness by SARS-CoV-2;
14. Develop a predictive model of infection and/or illness by SARS-CoV-2;
15. Identify socio-demographic factors, life habits, associated diseases and previous vaccinations associated with immune response and the risk of COVID-19 infection.

With a view to the approval of specific vaccines against COVID-19 for emergency use by ANVISA in January 2021 and incorporated by the National Immunization Program of the Brazilian Ministry of Health, the objectives for the subgroup of individuals who receive the intervention of this study with BCG or placebo and who are also immunized with specific vaccines against COVID-19 will be carried out in the part, taking into account in the future analysis, the time between the intervention of the study and vaccination against COVID-19, the vaccine used and the performance of the second dose of the vaccine used, aiming to identify a possible adjuvant effect of bcg vaccine as a stimulant

of cellular immunity, which also plays a role in immunopathogeny against SARS-CoV-2, including action prior to humoral response.

Furthermore, in cases of participants immunized with specific vaccines against SARS-CoV-2, the identification of asymptomatic infection by the virus, diagnosed through the conversion of serologies to COVID-19 in the moments M3 and M6 after the intervention, will not be evaluated, considering the bias caused by the use of vaccines against viral disease. In these cases, in order to characterize the diagnosis of COVID-19, there will be a need for a report (self-reported) of characteristic signs/symptoms associated with detection of SARS CoV-2 by RT-PCR.

METHODOLOGY:

Study Definitions:

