- **Health Professional:** For the purposes of this study, in addition to the definition of a health professional established in Resolution 218 - 97 - Regulation of health professions, the Brazilian Classification of Occupations will be used, and in an expanded way will be included undergraduate students in the area of health sciences who attend the hospital and are in direct contact with patients. Administrative technical professionals who circulate or perform activities in sectors within the hospitals participating in the study and who have direct contact with patients may also be included in the study, such as receptionists, maqueiros, security guards, among others.

Study Design:

The project proposes to monitor research participants for 6 months and thus conduct a controlled clinical trial, phase II-B, which compares the occurrence of SARS-CoV-2 infection as well as the time to infection among health professionals receiving bcg vaccine (experimental group) compared to those receiving placebo (control group). Coupled with the clinical trial, participants will also be analyzed in an observational study of two cohorts of volunteers, vaccinated with BCG and not vaccinated. In this part of the

study, participants will be analyzed in relation to the inflammatory profile, considering biomarkers predicting infection and evolution to severe form of COVID-19.

Study site:

The possible participants of this research will be recruited in two hospitals in the city of Rio de Janeiro (Hospital Complex Institute of Chest Diseases - Clementino Fraga Filho University Hospital of UFRJ and Pedro Ernesto University Hospital Complex - Piquet Carneiro Polyclinic of UERJ) and a hospital in the city of Barueri in SP (Hospital Municipal [name] - Barueri/SP).

Eligibility criteria:

Health professionals (according to the definitions of this study), who are in the exercise of their activities in the units of the study or not, of both sexes over the age of 18 years and who agree to participate in the study by signing the Informed Consent Form (TCLE).

Inclusion criteria:

1. Individuals aged 18 ≥, male or female, not infected with SARS-CoV-2
2. Agreement to participate in the study by signing the TCLE
3. Not being pregnant in case of women able to become pregnant

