4. Have not received a specific vaccine against COVID-19 or, if vaccinated against SARS-CoV-2, have received the complete immunization schedule only with vaccines approved by ANVISA and implemented by the National Immunization Program, (including the second dose) within a minimum of 15 days prior to the date of inclusion in the study
5. If the participant have not received a specific vaccine against COVID-19 approved by ANVISA, be aware and agree to be able to receive them only 15 days after the intervention proposed in this study

Exclusion criteria:

1. Professionals with a history of sars-cov-2 confirmed infection through RT-PCR or who have already presented clinical and molecular diagnosis of COVID-19 prior to the study

2. Individuals who have not undergone confirmatory tests for COVID-19
3. Breastfeeding
4. Individuals who report having primary or acquired immunodeficiency
5. Individuals who report being affected by malignant neoplasms
6. Patients reporting treatment with high-dose corticosteroids (equivalent to the prednisone dose of 20 mg/day or more) for more than two weeks
7. Patients who report being on other immunosuppressive therapies (antineoplastic chemotherapy, radiotherapy, among others)
8. Individuals who report being diagnosed with autoimmune diseases
9. Dermatological conditions at the vaccine site or generalized
10. Individuals who report being treated for active tuberculosis
11. Individuals who report a history of previous treated tuberculosis
12. Individuals with febrile symptoms (body temperature $\geq 37.5^{\circ}\text{C}$ in the last 48h)
13. Participation in other clinical prevention trials for COVID-19 (vaccines already approved by ANVISA for use by the National Immunization Program are not included in this item)
14. Report of vaccination with live microorganism administered in the month prior to randomization
15. Require that, if another vaccination with live microorganism is required, it is administered in the month following randomisation (If the other live vaccine can be administered on the same day, this exclusion criterion does not apply)
16. Known anaphylactic reaction to any ingredient in bcg vaccine
17. Adverse reaction prior to BCG vaccine [significant local reaction (abscess) or suppurative lymphadenitis]
18. BCG vaccine administered in the last year

Intervention Plan:

Intervention:

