It is estimated that it will take 376 individuals in each of the comparison groups to ensure a statistical power of 80% and a type I error of 5%, considering an incidence of SARS-CoV-2 infection of 20% in BCG vaccinated, 30% in unvaccinated, 15% in covid-19 vaccinated. It is expected a reduction in the joint effect of BCG with the COVID-19 vaccine between 10% and 15% and that the percentage of people vaccinated with BCG in the cohort is 50% and the percentage of people vaccinated for Covid-19 in the cohort is 80%.

We will also use for the two outcomes (below) the sequential design the groups are followed up until there is a group with clear benefits or that both groups do not present difference. This design is used when the results need to be known very quickly. If there is a large difference between the treatments, then this study will be performed in a shorter time when compared to the parallel trial. The main ethical advantage is that if one treatment shows a superiority over the other, the study can already be stopped. However, the interim analyses will be previously planned, in such a way that the calculation of sample size allows the multiplicity of the tests. The meaning of p-values in sequential analyses also changes, because when using sequential analyses, more than one analysis is performed, and the typical definition of a p-value as data "at least as extreme" as observed needs to be reset. One solution is to sort the p-values of a series of sequential tests based on the downtime and at what time the test statistic was in a certain appearance, known as ordering.

OUTCOMES:

Primary Outcome

1. Compare the cumulative incidence of SARS-CoV-2 infection

It is estimated that it will take 376 individuals in each of the comparison groups to ensure a statistical power of 80% for the detection of a difference in effects of 10%, considering that the control group will have an accumulated incidence of SARS-CoV-2 infection of 30% after 6 months of follow-up, for a type I error of 5%.

2. Compare the cumulative incidence of severe forms of COVID-19

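### Secondary objective 1 asks whether BCG delays disease, but the plan gives it only risk-ratio models, with no time-to-event method, time origin or censoring rule

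*Combined protocol and SAP*

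**What the plan says.** Two places pose a question about time. Epidemiological secondary objective 1 is to "Estimate whether BCG vaccination compared to placebo prolongs the time to the first respiratory disease proven by SARS-CoV-2". The Study Design section says that the trial "compares the occurrence of SARS-CoV-2 infection as well as the time to infection among health professionals receiving bcg vaccine".

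The Statistical Analysis Plan assigns one family of methods to every outcome: "logistic regression or Poisson models with robust variance will be used to evaluate the effect of BCG vaccine on primary and secondary outcomes". On the effect measure it says: "Associations will be expressed in the form of risk ratios and respective 95% confidence intervals". On timing it says: "These analyses will occur when the last enrolled research subject has completed 30 days and 6 months of preventive treatment". Random-forest imputation is the only provision for missing data. The combined document contains no Kaplan-Meier, log-rank, Cox, restricted-mean or person-time method, no start of the clock and no censoring rule.

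On COVID-19 vaccination the document says more. Inclusion criterion 4 admits people already vaccinated, who must "if vaccinated against SARS-CoV-2, have received the complete immunization schedule only with vaccines approved by ANVISA". Study visits allows vaccination after the study injection. The paragraphs that close Secondary Objectives, together with Study visits, stop using serology to diagnose asymptomatic infection in vaccinated participants; the former also require reported symptoms plus a positive RT-PCR. The same paragraphs plan an analysis of the vaccinated subgroup, "taking into account in the future analysis, the time between the intervention of the study and vaccination against COVID-19".

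**The concern.** A risk ratio at a fixed time compares how many people became ill by then. Objective 1 asks how much later they became ill. Protection that comes early and fades, and protection that comes late, can give the same 6-month risk ratio with quite different amounts of delay. Followed as written, the plan would answer the time question with the wrong kind of estimate, or leave the method to be chosen after the data are seen.

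Vaccination adds to this. Sample size assumes that 80% of the cohort will be vaccinated against COVID-19, without saying what share before entry. Under Blinding, a participant unblinded on request and found to have had placebo may be vaccinated before the 15-day wait ends, so vaccination timing could differ by arm. Ignoring vaccination, stratifying by it, censoring at it and adjusting for it over time answer different questions. The plan does not choose among them.

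**Working it through.** **The plan's own counts.** Inputs from Sample size and Outcomes: 376 per arm, 80% vaccinated against COVID-19, infection risk 30% with neither vaccine, 20% with BCG only, 15% with COVID-19 vaccine only, and a 10% to 15% joint reduction (15% reproduces the stated counts).
- Placebo: 376 × 0.2 × 0.30 = 22.6 and 376 × 0.8 × 0.15 = 45.1. The plan states 23 and 45, total 68.
- BCG: 376 × 0.2 × 0.20 = 15.0 and 376 × 0.8 × 0.15 × 0.85 = 38.4. The plan states 15 and 38, total 53.

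The control risk used below is 68/376 = 18.1%. It is an any-infection rate, because the plan gives none for proven disease.

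**Same risk ratio, different delay (illustration).** Assume a constant control hazard and no dropout: λ = −ln(1 − 0.181)/180 = 0.001108 per day. Disease-free time to day 180 is the area under the survival curve.
- Control: 0.1809/0.001108 = 163.2 days.
- BCG halves the hazard in months 0-3 only: risk = 1 − exp(−45λ − 90λ) = 13.9%, ratio 0.139/0.181 = 0.77. Area = (1 − e^(−45λ))/(0.5λ) + e^(−45λ)(1 − e^(−90λ))/λ = 87.8 + 81.5 = 169.3 days, a gain of 6.1.
- BCG halves the hazard in months 3-6 only: the exponent is again 135λ, so the ratio is again 0.77. Area = (1 − e^(−90λ))/λ + e^(−90λ)(1 − e^(−45λ))/(0.5λ) = 85.7 + 79.5 = 165.1 days, a gain of 1.9.

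Repeating this at other control risks:

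| Control risk | 6-month ratio, early and late | Days gained, early | Days gained, late |
|---|---|---|---|
| 18.1% | 0.77 | 6.1 | 1.9 |
| 30% | 0.78 | 10.1 | 3.1 |
| 9.0% (half of 18.1%) | 0.76 | about 3.1 | 1.0 |
| 15% (half of 30%) | 0.77 | 5.1 | 1.6 |

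The last two rows assume that half of infections are proven disease.

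**What a day-30 ratio would add.** At 18.1%, control cases by day 30 are 376 × (1 − e^(−30λ)) = 12.3. BCG cases are 376 × (1 − e^(−15λ)) = 6.2 in the early scenario (ratio 0.50) and 12.3 in the late one (ratio 1.00).

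**Precision of a restricted mean difference.** As a harder test, assume delay with full catch-up: the hazard is cut by 30% or 50% to M3, then raised by the same fraction. The 6-month ratio is 1.00 throughout. The gain is 2.5 to 6.9 days across control risks of 18.1% and 30%. With 376 per arm, two-sided 5%, and SE = √[(var_BCG + var_control)/376], the 50% case at 18.1% gives 4.13/2.78 = 1.49 standard errors, or 32% power. Across the four cases power is about 14% to 52%. If half of infections are proven disease, the gain is 1.2 to 3.4 days and power 9% to 27%.

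**The case against.** The primary comparison is cumulative incidence, for which a risk ratio is suitable, and time to disease is one of 15 secondary objectives. A Poisson model could also carry a person-time offset. The first point stands and limits the reach of this one. The second does not: no offset is stated, and the stated measure is a risk ratio, not a rate ratio.

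A reader might infer that the plan could not tell early from late protection at all. The documents do not support that. If the 30-day and 6-month wording means risk at two times, the day-30 ratio separates the two scenarios. It would rest on about 6 versus 12 cases and would still not estimate delay. If the wording instead means calendar looks set by the last participant, follow-up at the first look is unequal: with uniform enrolment over the Schedule dates (an assumption), (180 − 30)/427 = 35%, or 264 of 752, would be short of 180 days. Even then a 30-day risk needs no rule for staggered entry; only a longer horizon does.

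A reader might also infer that COVID-19 vaccination during follow-up is not handled. It is, in part, through the serology rule, the requirement for symptoms plus RT-PCR, and the subgroup plan.

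The catch-up scenarios need BCG recipients to have a higher hazard than placebo after M3, which nothing in the document suggests. They serve here only to show precision. Leaving the choice between logistic and Poisson open is mainly missing detail, since the plan already fixes the risk ratio as its measure.

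**Conclusion.** The point holds in a limited form. A stated time-to-disease objective and a stated time-to-infection comparison have no matching analysis, time origin or censoring rule, and the models assigned to all outcomes cannot estimate delay. In the early-versus-late illustration, one 6-month ratio of 0.76 to 0.78 covers gains from about 1.0 to 10.1 days, depending on timing and control risk. Those figures assume piecewise-constant hazards, no dropout and infection rates borrowed from the plan; they show what the ratio hides and do not predict the trial's result.

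On vaccination, the gap is only that no rule says how vaccination during follow-up enters the efficacy or time-to-disease analysis. The primary cumulative-incidence analysis is not put in doubt by this point. The change should be made, but the trial does not depend on it.

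**What to change.** For secondary objective 1, replace the risk-ratio model with:
- Kaplan-Meier curves by arm, from the date of intervention to symptom onset of RT-PCR-proven disease, censored at loss to follow-up or M6.
- The restricted mean time difference to 180 days with a 95% confidence interval, presented as an estimate rather than a test. A Cox hazard ratio is optional, because it also hides timing (0.74 versus 0.76 in the early and late scenarios at 18.1%).
- A vaccination rule. Main analysis: follow-up continues after COVID-19 vaccination, stratified by vaccination at entry. Sensitivity analysis: censoring at the first dose during follow-up, which may be informative. Tabulate vaccination timing by arm.

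If time to any infection is also analysed, its event definition must allow for serology no longer counting after vaccination. State whether 30 days and 6 months are risk times or calendar looks. Keep the risk ratio for the cumulative-incidence outcomes.

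The cost is SAP wording and one standard analysis, with no new visits. Besides the limited power, onset dates may be coarser after M3: the Study visits text gives monthly contact, while the M4/M5 row of the visit table mentions weekly email. These must be reconciled. RT-PCR is obtained through outside services, so confirmation depends on their records.
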